## **5 Study Design**

A randomized, double-blind, placebo-controlled pilot study of netazepide, a cholecystokinin-2 receptor antagonist, in patients with Barrett's esophagus without dysplasia. Patients will take netazepide or placebo for 12 weeks.

There are 2 research sites, Columbia University and the MRC Cancer Unit at the University of Cambridge.

Patients will be randomised (1:1 ratio) to receive either 25 mg netazepide or matching placebo.

## 6 Time and Events Table

	Baseline Testing/ Prestudy Evaluation		Study treatment		Follow-up period
	Visit 1 	Visit 2	Week 6 visit	Week 12 visit	Follow-up
Evaluation/ Procedure	Registration	Randomization, & Endoscopy	Week 6	Week 12	Follow Up Visit 4 weeks after stopping treatment
Informed consent	X				
Assess eligibility	X				
Central pathology review 	X				
Medical history	X				
Physical exam	X				
Vital signs	X	X 	X	X	X
Height and weight/ waist circumference	X				
Smoking history	X				
Medication history	X				
Blood and urine collection for safety tests	X	X 	X	X	X
Urine pregnancy test 	X	X 	X	X	X
ECG	X	X 	X	X	X
Blood for YF476 assay 			X	X	
Blood for assay of fasting serum gastrin and plasma CgA, and serum for storage		X	X	X	X
EGD (Upper GI endoscopy)		X		X	
Biopsies		X		X	
Concomitant medication assessment		X	X	X	
Dispense study medication		X	X		
Collect study medication			X	X	
Compliance assessment			X	X	
AE assessment		X	X	X	X

1. There may be up to a 2-week gap between Visits 1 and 2.
2. Review of patient's history to obtain histological confirmation of the patient's eligibility to participate in the trial.
3. Plasma YF476 assay: patients fast overnight. For the Week 6 and 12 visits, patients bring their container of study medication with them, and take study medication only after collection of blood samples for trough YF476, fasting serum gastrin and CgA levels, and endoscopy (if applicable). Patients stay for 1 h after dosing for collection of a blood sample for peak YF476 level.
4. Pre-menopausal women only.
5. These tests may be omitted if Visit 2 occurs on the same day as Visit 1.

## **7 Planned Analyses**

### **7.1 Interim Analyses**

No interim analyses are planned.

### **7.2 Final Analysis**

The database will be locked once all patients have completed the study, data have been entered and all queries resolved. The final analysis will be carried out following database lock and unblinding.

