7.7 Blinding and unblinding methods

- Bottles containing study medication for individual patients will not be labelled with any information to indicate whether the capsules are YF476 or placebo.
- Patients will be blinded to study treatment.
- One member of the HMR Statistics and Data Management Department will not be blinded. That person will generate the randomization code. The Columbia University biostatistician will be blinded.
- All Investigators will be blinded to study treatment.

-
- For each site, there will be a blinded monitor and an unblinded monitor. The unblinded monitor will review dispensing records at the site Pharmacy.
 - Pharmacy staff will not be blinded.
 - The Data and Safety Monitoring Board will not be blinded.
 - The blind will be broken by the investigator or delegate in the following circumstances:
 - If unblinding is required in the interest of the safety of a subject, an investigator will discuss the matter with the sponsor before opening the individual code-break envelope for that subject. In a medical emergency, the principal investigator or delegate may open the individual code-break envelope for that subject without prior consultation with the sponsor. In that event, the principal investigator or delegate will notify the sponsor as soon as possible that the randomisation code has been broken for the subject.
 - The blind will be broken for the entire study population at the completion of the study, after the statistical analysis plan (SAP) has been signed and the database has been locked.

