8.7 Withdrawal of patients from the trial

8.7.1 *Termination of study medication*

Patients may stop taking study medication for the following reasons.

- When a patient has completed the protocol-prescribed treatment, we will not provide any further study medication.
- If a patient has an adverse event, grade 2 or greater (see section 11.1), the patient or investigator may choose to terminate study treatment.
- A patient might be non-compliant and stop taking the protocol-prescribed treatment; or the investigator may choose to terminate study treatment.
- The investigator may terminate study treatment because of a medical contraindication.
- The investigator may terminate study treatment because of evidence of serious interactions with medications metabolized by CYP3A4/5 or CYP2C8, (see Appendix B for list of relevant medications).

In all cases listed above, patients will continue to be followed, if possible, for safety reasons and in order to collect endpoint data according to the schedule of events.

8.7.2 **Termination of study participation**

Patients may go 'off-study' (ie leave the study with no follow-up possible) for the following reasons.

- The protocol treatment and any protocol-required follow-up period is completed.
- If a patient has an adverse event, grade 2 or greater (see section 11.1), the patient may choose to terminate study participation.
- A patient might be lost to follow-up, if the investigator is unable to establish contact with him or her.
- A patient might be non-compliant and not attend the clinic visits (including the follow-up visit).
- The investigator may terminate study participation because of a medical contraindication.
- A patient may withdraw his or her consent to participate in the study.
- Determination of ineligibility, not discovered before enrollment. In particular; patients will be withdrawn from the study if their baseline endoscopy (Visit 2):
 - does not show any intestinal metaplasia; or
 - biopsies are read as indefinite for dysplasia, low grade dysplasia, high grade dysplasia, or adenocarcinoma.
- Death.

8.8 **Study termination**

Enrollment of patients onto the study will be terminated when at least 20 participants have completed 12 weeks of treatment, undergone a post-treatment endoscopy, and returned for the follow-up visit (4 weeks after stopping study medication). The study will end when the analysis of all biopsy samples is complete.

9 **Criteria for evaluation and endpoint definition**

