10.3.2 Collection and handling procedures

- *Collection and analysis of tissue for RNA-Seq, IHC and qRT-PCR*

RNA-Seq and qRT-PCR. Routine endoscopic biopsies (4 quadrant biopsies every 2 cm along the length of BE) will be taken for clinical purposes and placed in formalin. The formalin-fixed biopsies taken at CUMC will be submitted to the Columbia University Department of Pathology (CUDP). The formalin-fixed biopsies taken at NIHR CIW will be stored there; slides of the biopsies will be sent by courier to CUDP at the end of the study, or as agreed between the investigators and sponsor. The respective Departments of Pathology will store the paraffin-embedded samples as per usual practice. Histologic analysis of biopsies from both study sites will be done at CUDP. As per clinical practice, these biopsies will be reviewed to assess the presence of dysplasia. Six additional biopsies (from each endoscopy; 2 biopsies each from GE junction, mid-Barrett's segment, and normal esophagus) will be taken for study purposes, placed in Qiagen Allprotect™ tissue reagent, and then stored at -80°C for future RNA-Seq and qRT-PCR analysis. The freezers for storing these samples are located in the laboratory of [name] at Columbia University. Samples taken at Cambridge University will be stored in freezers in [name] laboratory at the MRC Cancer Unit, University of Cambridge, until dispatch to Columbia University.

IHC analyses. Additional sections will be cut from paraffin-embedded endoscopic biopsies for study purposes. Slides from NIHR CIW will be sent by courier to Columbia University at the end of the study, or as agreed between the investigators and sponsor.

Ki67 expression will be assessed by IHC from esophageal biopsies of Barrett's esophagus. Paraffin-embedded biopsies from the most distal esophageal biopsies containing intestinal metaplasia will be immunostained for Ki67. Ki67 index will be calculated as: (# crypt epithelial cells with positive nuclear staining for Ki67) / (# BE crypt cells counted). Five representative crypts with goblet cells will be evaluated from five separate fields at 100x magnification. Δ Ki67 for YF476 and placebo arms will be compared. The pathologist evaluating Ki67 staining will be blinded to both treatment arm and timing of endoscopy (ie pre- or post-treatment).

- *Collection and processing of blood samples for laboratory safety tests:*

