### **3 Introduction**

This Statistical Analysis Plan (SAP) is based on the current trial protocol (version 24, 26 April 2018). Where statistical methods differ substantially between this SAP and the protocol, that will be identified in this document.

This SAP describes the datasets and the statistical methods to be used for the reporting and analysis of all data collected during the trial except the efficacy data which will be reported separately. Serum gastrin and plasma CgA data will be included in this SAP.

The randomisation code will not be broken before this SAP is finalised. If a future protocol amendment necessitates a substantial change to the statistical analysis of the trial data, this SAP will be amended accordingly. If, after database lock, additional analyses are required to supplement the planned analyses described in this SAP, those unplanned analyses will not be described in an amended SAP, but they will be identified in the integrated clinical study report (CSR). Any deviations from this SAP will be documented in the CSR.

This SAP has been written in consideration of the following guidelines:

- International Conference on Harmonization (ICH) E9, Guidance for Industry: Statistical Principles for Clinical Trials (ICH E9 1998); and
- ICH E3, Guidance for Industry: Structure and Content of Clinical Study Reports (ICH E3 1995).

Statistical analysis will be done using SAS® 9.3 on a Windows PC.

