**Template T\_LB2**

Table 14.3.5.xx Summary of Chemistry Laboratory Values

Laboratory Test (units)	Treatment	Visit	n	Mean	SD	Median	Min	Max	n	Change from Baseline				
										Mean	SD	Median	Min	Max
	Treatment 1 (N=xx)													

Source: Listing 16.2.xx

*Programming notes:* Continued with all treatments and time points For Ki67 Expression data exclude first column

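### SAP 7.2 lets the code be opened once patients have finished and data are entered, while protocol 7.7 with 8.8 holds it until all biopsies are analysed; nothing in the SAP requires Ki67 to be locked first.

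*SAP*

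**What the plan says.** **Timing in the SAP.** Section 7.2 reads "The database will be locked once all patients have completed the study, data have been entered and all queries resolved". It continues: "The final analysis will be carried out following database lock and unblinding". Biopsy reading is not named. Section 3 adds "The randomisation code will not be broken before this SAP is finalised".

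**Scope of the SAP.** Section 3 says the SAP covers "all data collected during the trial except the efficacy data which will be reported separately", and then brings serum gastrin and CgA back in. Section 15 analyses only those two markers, and section 4.3 rules out formal testing. The output list in section 19.1 has no Ki67 table; the one trace is a programming note in template T_LB2, "For Ki67 Expression data exclude first column". Section 9 nevertheless assigns the primary endpoint to the ITT population.

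**Timing in the protocol.** Section 7.7 states "The blind will be broken for the entire study population at the completion of the study", and also requires a signed SAP and a locked database. Section 8.8 states "The study will end when the analysis of all biopsy samples is complete".

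**Slides.** Histology and Ki67 for both sites are read at Columbia. For Cambridge, protocol 10.3.2 says "slides of the biopsies will be sent by courier to CUDP at the end of the study", or at another time agreed between the investigators and the sponsor.

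**Declared changes.** SAP 17 lists one change from the protocol, the dropped PK analysis set.

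**The concern.** The two documents name different events as the trigger for opening the code, and the primary endpoint sits in the gap between them. The protocol's safeguards are a signed SAP and a locked database. Under the SAP's wording both can be satisfied by a SAP with no Ki67 analysis and by a lock that is not required to include Ki67 reads.

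If the code is opened at that point, several decisions about Ki67 could still be pending and could be taken by people who know the arms: whether a biopsy has enough intestinal metaplasia or enough crypts to count, whether a slide is re-read, and whether late histology moves a patient out of the per-protocol set. In a trial of 20 patients one such decision can change the result, and an early unblinding cannot be undone.

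**Working it through.** **1. The triggers side by side**

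| | SAP | Protocol |
|---|---|---|
| Event that opens the code | All patients completed, data entered, queries resolved, lock (7.2) | Completion of the study, plus signed SAP and lock (7.7) |
| Are biopsy reads required first? | Not stated | Yes, if completion in 7.7 means the study end in 8.8 |
| Which SAP must be final? | This one (3), which leaves out Ki67 | The SAP, written on the footing that it covers the final analysis (13.2) |

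A patient's completion and the study's end are different events in the protocol. Section 8.7.2 has a patient leave when treatment and follow-up are done, and section 4.1 gives 16 to 18 weeks per patient. Section 8.8 puts the study end at the last biopsy analysis. SAP 7.2 uses the patient-level event.

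**2. Can Ki67 reads be late?** The default time for sending Cambridge slides is the end of the study. If that has its 8.8 meaning, it is circular, because slides sent when the study ends cannot be read before it ends. If it means the last patient's completion, it coincides with the SAP's lock trigger. Only the alternative of an agreed earlier date avoids both.

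**3. What is already fixed?**
- Test: two-sample t-test on the change in Ki67 as primary, ANCOVA with baseline as sensitivity (protocol 13.4).
- Population: ITT (SAP 9).
- Missing data: observed data only, no imputation (protocol 13.2).
- Reading: pathologist blinded to arm and to timing of endoscopy (protocol 10.3.2).

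**4. What is not fixed?**
- ITT entry needs one post-baseline assessment, not a readable pair of biopsies. No rule covers unreadable or insufficient samples.
- Protocol 8.7.2 withdraws patients on baseline histology, and SAP 13.2 counts unmet entry criteria, or a missed withdrawal, as a major deviation. Per-protocol membership can therefore depend on late-read slides.
- SAP 3 says analyses added after lock will be identified in the study report but not described in an amended SAP.

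**5. Size of the worst case**

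The plan's own power figures come first, with 10 per arm, two-sided 0.05 and 18 degrees of freedom. The noncentrality is difference / (SD × √(2/10)).
- Difference 0.30, SD 0.16: 0.30 / (0.16 × 0.4472) = 4.19, power 97.7% (stated 98%).
- Difference 0.25, SD 0.14: 0.25 / (0.14 × 0.4472) = 3.99, power 96.5% (stated 97%).

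All nine cells of Table 1 reproduce, so 10 per arm and an SD of 16 points are a sound base.

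Next, trials with no drug effect were simulated: 10 per arm, normal data, SD 16 at each visit, and an assumed correlation of 0.5 between visits. The SD of the change is then 16 × √(2 × (1 − 0.5)) = 16. Each trial was tested once on all 20 patients, then again with each patient left out in turn, keeping the smallest p-value.

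| Run | Fixed t-test, p ≤ 0.05 | Any one of 20 patients dropped |
|---|---|---|
| 8,000 trials | 4.6% | 14.5% |
| 8,000 trials, repeated independently | 4.9% | 15.2% |
| 4,000 trials | 4.7% | 14.9% |

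The simulation standard error for the first deletion figure is √(0.145 × 0.855 / 8,000) = 0.4 points, so the runs agree. These rates count significance in either direction. Counting only results that favour the drug gives about 7.7% against a nominal 2.5%. The deletion figure does not depend on the assumed SD or correlation, because the t statistic on the change does not depend on scale; it depends on 10 per arm and normal data.

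**The case against.** There is a good case that the plan is safer than SAP 7.2 alone suggests.

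- **The protocol governs timing.** SAP 3 says the SAP is based on the protocol and will identify substantial differences, and SAP 17 declares none on unblinding. Read that way, the slides are analysed before the code is opened. This stands as a likely intention, but SAP 7.2 is the operative instruction and says something else.
- **Finalising this SAP is not the only condition.** SAP 3 states it as a necessary condition. A reader might infer that it is sufficient; the text does not say so.
- **Exclusions are reviewed before lock.** SAP 13.2 requires this, and the ITT and PP rules are written down. It stands for deviations known by then. It does not mention biopsy evaluability and cannot use histology not yet read.
- **The test is not open to choice.** A reader might infer that an unblinded team could pick the better of t-test and ANCOVA. Protocol 13.4 names which is primary, so a switch would be a visible departure. Adding that choice raises the simulated ceiling by only about one point (14.5% to 15.3% in the first run).
- **Slides would not be read unblinded.** The pathologist is blinded to arm and visit, which controls measurement bias. This stands in full.
- **The locked database may contain Ki67.** A reader might infer that it does not. SAP 3 limits what this SAP analyses and reports; it does not describe the database.
- **A separate Ki67 plan may exist.** The text of SAP 7.2.1, on who is responsible for the analysis, was not available. One can say only that neither document mentions such a plan.

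**Conclusion.** The conflict is real and undeclared. Followed literally, SAP 7.2 allows the code to be opened before Ki67 reads are locked and before any signed SAP in these documents covers the primary endpoint. This takes completion of the study in protocol 7.7 to be the study end in 8.8, which is the natural reading but is not spelled out.

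The remaining exposure is narrow: evaluability of biopsies, re-reads, and per-protocol membership that turns on late histology. The documents do not support the stronger claims that the primary endpoint would be read unblinded or that its analysis is unspecified.

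The figure of about 15% is a ceiling. It assumes that a team knowing the arms tries all 20 single deletions and keeps the best, which no section permits. It shows how much one decision can matter at this sample size and does not predict the trial's error rate. The point merits correction because the remedy is cheap and early unblinding is irreversible.

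**What to change.** Amend SAP 3 and 7.2 to match protocol 7.7 and 8.8, so that the code is not broken until both conditions hold:

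1. Ki67 reads from both visits and both sites are complete, checked and locked, with biopsy evaluability and ITT and PP membership signed off.
2. The Ki67 analysis of protocol 13.4 (ITT, two-sample t-test with 95% confidence interval, ANCOVA as sensitivity) is in this SAP or in a signed companion SAP to which this one refers.

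Record the point in SAP 17, and either complete or delete the Ki67 note in template T_LB2.

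The cost is one paragraph, a short Ki67 section and an entry in SAP 17. The unblinded safety and PK tables wait for the slide reads. If safety results are needed sooner, they can be shown pooled over arms. Individual netazepide concentrations can reveal the arm, so they should stay away from anyone deciding on Ki67 evaluability until the reads are locked.

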## **8 Sample Size Considerations**

### **8.1 Sample Size Assumptions**

Based on preliminary data, a mean baseline Ki67 index of 45–50%, with a common SD of 14–18% was estimated. Assuming a two-sided type I error rate of 0.05, a sample size of 20 (10 per arm) has 98% power to detect a 30% absolute difference in  $\Delta$ Ki67 between the two arms if the common SD is 16%, and 97% power for a 25% difference with a 14% common SD (see Table 1).

Table 1. Power calculations based on 20 patients (10 per arm)			
	<math>\Delta\text{Ki67}_{\text{YF}} - \Delta\text{Ki67}_{\text{pl}}</math>		
SD	0.25	0.30	0.35
0.14	97%	99%	>99%
0.16	91%	98%	>99%
0.18	84%	94%	98%

## 9 Analysis Populations

The following populations will be identified:

Screened Population: All patients screened for the study.

Safety Population: All patients who are randomised and received at least one dose of the study drug. In this population, treatment will be assigned based upon the treatment patients actually receive regardless of the treatment to which they were randomized.

Intent-to-Treat (ITT) Population: All randomised patients who receive at least one dose of study medication and had at least one post-baseline assessment. In this population, treatment will be assigned based upon the treatment to which subjects were randomised regardless of which treatment they actually received.

Per Protocol (PP) Population: All randomized patients who receive at least one dose of study medication and had at least one post-baseline assessment and did not have any major protocol deviations.

In all populations (apart from ITT) treatment will be assigned based upon the treatment patients actually receive regardless of the treatment to which they were randomised.

The primary endpoint will be analysed using the ITT population.

### 9.1 Analysis Datasets

All analysis datasets will be based on observed data, except as outlined in Section 12.2.

## **10 Treatment Comparisons**

The treatment comparison of interest is active (netazepide) versus placebo.

## **11 General Considerations for Data Analyses**

### **11.1 Data Display Treatment and Other Subgroup Descriptors**

The sort order for treatment groups will be placebo, then study treatment. When a total column is included, it immediately follows the treatment groups which it aggregates.

Listings of data will be sorted and displayed by treatment group, patient number, and also by date and time if applicable.

The treatment descriptions to be used on all tables and listings are:

#### **Treatment Groups**

Placebo

Netazepide 25 mg

### **11.2 Conventions for Summary Statistics and Data Displays**

The minimum set of summary statistics for numeric variables will be: n, mean, standard deviation (or standard error), median, minimum, and maximum. 95% confidence intervals will be presented where appropriate for data interpretation.

Categorical data will be summarised in frequency tables with n and percentage. Summaries of a categorical variable will include all recorded values.

The minimum and maximum values will be presented with the same number of decimal places as the raw data collected on the CRF (or to 3 significant figures for derived parameters less than 100 and as integers for values more than 99). The mean and percentiles (e.g. median, Q1, and Q3) will be presented using one additional decimal place. The standard deviation and standard error will be presented using two additional decimal places.

## **12 Data Handling Conventions**

### **12.1 Premature Withdrawal and Missing Data**

All patients who withdraw prematurely from the study or study drug will be included in the statistical analyses.

If a patient completes the treatment period but has missing data, then this will be made apparent in the patient listings. Missing data will not be imputed except for as outlined in Section 12.2.

If the study is prematurely discontinued, all available data will be listed and a review will be carried out to assess which statistical analyses are still considered appropriate.

Data collected at unscheduled time points during the study will not be used in the summaries or data analyses. They will be included in the listings.

If time information (i.e. hours and/or minutes) for adverse events or concomitant medication is missing, but the day is present, then the time will be calculated in days. If date information is partial or missing, then any derived times (e.g. AE start time from last study medication) will be listed as missing.

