4.3 Risk-benefit analysis

What are the potential risks of harm to the trials patients from YF476 and from the trial procedures, and how might they be mitigated?

Reported adverse events and potential risks

In all studies in healthy volunteers, YF476 was well tolerated. Adverse events were minor, transient, occurred in subjects given placebo or comparators as well as YF476, and were not YF476-dose dependent. YF476 did not affect: vital signs; ECG; or safety tests of blood and urine. There was no evidence of effect on QT interval in human studies, but *in vitro* studies showed that YF476 has a low potential for prolonging QT interval (See Section 3.2.1). So, until we have more information about YF476, patients with prolonged QT interval are excluded from clinical trials.

The adverse effects that occurred at a frequency of 10% or greater were: abdominal distention, diarrhea, abdominal pain, nausea, and headache. None of these adverse effects were observed with greater frequency as compared to placebo or comparators.

Because of the pancreatic findings in the 13-week toxicology study of dogs (Section 3.2.1), serum amylase and lipase will be monitored at each visit. Also, any patient who complains of abdominal discomfort at any time during the study will be seen immediately by the investigator or delegate and evaluated with history, physical examination, and laboratory tests, including serum amylase and lipase, and other appropriate tests, including radiological investigations.

Risk from concomitant medications

In vitro studies have shown that the likelihood of a drug-drug interaction in patients *in vivo* is:

- CYP2C8: possible for 50–400 mg YF476
- CYP3A4 (testosterone): remote for 50 & 100 mg YF476, and possible for 200 & 400 mg
- CYP3A4 (midazolam): remote for 50 mg YF476, and possible for 100–400 mg.

Although YF476 caused some irreversible inhibition of CYP3A4, the degree of inhibition makes a drug-drug interaction in patients *in vivo* unlikely. And, a clinical study (T-007) of YF476 and midazolam (a substrate of CYP3A4) alone and in combination showed that neither medicine affects the pharmacokinetics of the other (see YF476 Investigator's brochure for further details).

Many medicines are metabolised via CYP3A4/5. Very few are metabolised via CYP2C8. Examples of the main types of medicine that are metabolised by CYP3A4/5

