13.6.2 Analyses of Clinical Laboratory Tests

Standard haematology, biochemistry and urinalysis at each planned assessment, and change from baseline at each planned post-baseline assessment, will be summarized.

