13.6.3 Electrocardiogram Analyses

The ECG variables (PR, RR, QRS, QT, QTcB, and QTcF) and heart rate (HR) at each planned assessment will be summarised. The QT intervals will be corrected for heart rate by the Bazett's and Fridericia's formula ($QTcB = QT/[RR]^{1/2}$ and $QTcF = QT/[RR]^{1/3}$). The incidence of outliers in absolute QT, QTcF and QTcB intervals (>450, >480, and >500 msec), and the change from time-matched baseline in QT, QTcF and QTcB intervals (>30 and >60 msec) will be summarised.

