### **14.5 Clinical Laboratory Evaluations**

Data from haematology, clinical chemistry and urinalysis will be summarised by treatment group.

All laboratory values of potential clinical importance will be listed and all related laboratory results (i.e. haematology or clinical chemistry) for patients with values of potential clinical importance will be listed, separately. Frequencies of laboratory values of potential clinical importance will be summarised.

Urinalysis parameters will also be listed.

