#### **14.6.2 ECG**

QT interval data will be presented using Bazett's (QTcB) and Fridericia's (QTcF) corrections.

ECG data will be summarised by treatment and visit. Differences from baseline (Visit 2) will be summarised by treatment and visit.

The number of patients with a potentially clinically important ECG value will be summarised by actual treatment and visit, giving the numbers of patients with QT, QTcB or QTcF > 450 msec, > 480 msec and > 500 msec, and the numbers of patients with increases in QT, QTcB or QTcF from baseline of > 30 msec and > 60 msec. A supporting listing of all patients with an ECG value of potential clinical importance and a separate listing of ECG findings classified as abnormal by the Investigator will also be provided.

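### Off-visit amylase, lipase and ECG results are listed but left out of the by-arm tables of potentially clinically important values (SAP Tables 14.3.4 and 14.3.7.2)

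*SAP*

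**What the plan says.** SAP 12.1 sets the rule for extra data: "Data collected at unscheduled time points during the study will not be used in the summaries or data analyses". The next sentence says where the data go: "They will be included in the listings". There is no exception for safety counts.

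Protocol 4.3 responds to the pancreatic findings in the 13-week dog study in two ways. Amylase and lipase are measured at every visit. In addition, "any patient who complains of abdominal discomfort at any time during the study will be seen immediately by the investigator or delegate", with an evaluation that includes "laboratory tests, including serum amylase and lipase, and other appropriate tests, including radiological investigations".

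SAP 14.5 promises a laboratory count: "Frequencies of laboratory values of potential clinical importance will be summarised". This is Table 14.3.4, template T_LB1. SAP 14.6.2 promises an ECG count: "The number of patients with a potentially clinically important ECG value will be summarised by actual treatment and visit". This is Table 14.3.7.2, template T_EG3. Both templates are laid out by treatment and visit. Neither has an unscheduled row or a worst-value row.

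Under SAP 12.4 a laboratory value is potentially clinically important when it is marked clinically significant in the CRF. For QT, QTcB and QTcF the SAP sets numerical limits.

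**The concern.** Excluding unscheduled values is sound for by-visit means, where an extra sample has no visit to belong to. It suits a count of important values less well, because the question there is whether the value occurred, not when.

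The pancreas is the protocol's own named concern: Protocol 3.2.1 says that the dog study did not clearly establish a no-effect level. The for-cause testing exists to catch what the planned visits miss, yet what it finds between visits is kept out of the table that summarises important laboratory values by arm.

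Two features sharpen this. First, Protocol 6.6 has treatment discontinued when drug-related toxicity is suspected, and Protocol 8.7.1 continues follow-up on the ordinary schedule. A value that prompts stopping between visits is unscheduled, and the next value that counts may be off drug. Second, SAP 4.3 plans no formal testing, so the descriptive tables carry the between-arm safety comparison.

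**Working it through.** This is a question of following a rule through the tables. No stated figure in the plan bears on it apart from the planned 10 per arm (Protocol 13.7, SAP 8.1).

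**Step 1. Planned post-dose samples.** The schedule (Protocol 8.1, SAP 6) has laboratory tests and ECGs after dosing at Week 6, Week 12 and follow-up, which is three occasions. Patients are seen for abdominal discomfort at any time, so a triggered test may fall between these.

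**Step 2. Path of an off-visit amylase or lipase result marked clinically significant.**

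| Output | Does the result appear? | Basis |
|---|---|---|
| Listing 16.2.8.1 (important chemistry values) | Yes | SAP 12.1, 19.1 |
| Table 14.3.4 (count by arm and visit) | No | SAP 12.1; T_LB1 has no row for it |
| Tables 14.3.1.1 and 14.3.1.2 (treatment-emergent AEs by arm; drug-related ones) | Only if also recorded as an AE (for 14.3.1.2, judged drug-related) | Protocol 11 and 11.1; SAP 14.2 |

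SAP 19.1 names Listing 16.2.8.1 as a source of Table 14.3.4. A value can therefore stand in the source listing and be absent from the table drawn from it.

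**Step 3. Path of an off-visit ECG.** It appears in Listing 16.2.9.1 if it meets a QT limit, and not in Table 14.3.7.2. The difference from Step 2 is that Protocol 4.3 does not name an ECG among the triggered tests, so this part applies only if an extra ECG is done.

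**Step 4. How often planned visits would miss a transient rise (illustration).** The durations and the uniform onset are assumptions, not figures from the documents. Let onset be uniform over the 84 treatment days, let the rise last d days, and put the on-treatment visits on days 42 and 84. For d up to 42, the share that spans a visit is 2d/84.

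- d = 3: 6/84 = 7%, so 93% are missed.
- d = 7: 14/84 = 17%, so 83% are missed.
- d = 14: 28/84 = 33%, so 67% are missed.

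The follow-up visit, near day 84 + 28 = 112, does not change this. A 14-day rise that starts on day 84 ends on day 97.

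**Step 5. Weight of one patient.** 1/10 = 10 percentage points of an arm in a per-patient count. T_LB1 is by visit, and its programming note defines n as a number of results. T_EG3 carries the same note, although SAP 14.6.2 speaks of numbers of patients. The 10 points therefore describe the row proposed below, not a shortfall in an existing cell.

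**The case against.** The strongest reply is that the information is not lost.

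- **AE route.** Protocol 11 counts an abnormal laboratory finding as a possible AE, and Protocol 11.1 records all AEs after consent and treats clinically significant abnormalities among them. SAP 14.2 counts treatment-emergent AEs by arm, and the discomfort itself would be counted there. This stands, and it defeats the reading that such results can never reach a by-arm count. It does depend on the investigator entering the enzyme result as a separate event. If only the symptom is entered, the table shows abdominal pain and no enzyme rise.
- **Listings.** SAP 11.1 sorts them by treatment group, and in a trial of about 20 patients they can be read directly. This also stands, but a listing gives no incidence and does not alter a count.
- **Not every summary is closed.** Under SAP 12.2 a repeat taken before dosing becomes the baseline, and an out-of-range planned value is kept over its later repeat. Under SAP 12.3 safety data from visits outside the window are still used. A reader might infer from 12.1 alone that all extra results vanish from all summaries; these rules show otherwise.
- **Not every triggered test is unscheduled.** Discomfort reported at a planned visit is covered by that visit's amylase and lipase tests.
- **Agreement with the protocol.** Protocol 13.6.2 summarises "Standard haematology, biochemistry and urinalysis at each planned assessment", so the laboratory rule is no departure from it. The QT outlier sentence in Protocol 13.6.3 carries no such limit of its own, but that section opens with planned assessments, so a conflict cannot be claimed there either.
- **Equal ascertainment.** Planned samples are taken alike in both arms. Symptom-triggered samples may not be, so counting them can create a difference through detection alone. This is a real cost, and it is why the planned-visit rows should stay.

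**Conclusion.** The point holds as a gap in two safety tables. Unscheduled laboratory and ECG values are listed but not counted in Tables 14.3.4 and 14.3.7.2, so an off-visit amylase or lipase rise enters a by-arm count only through AE reporting. The laboratory part matters more, because the protocol itself creates the off-visit tests. The ECG part is conditional.

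A reader might go further and infer that the existing tables understate an arm's incidence by 10 percentage points. The documents do not support that. Table 14.3.4 is by visit, with n defined as results, and nothing shows how many off-visit abnormalities to expect. The 67% to 93% in the illustration rests wholly on the assumed durations and uniform onset, and it applies only to abnormalities that are transient. Nor do the documents show that the omission favours one arm; it would do so only if treatment changed the rate of symptoms.

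The change is still worth making, because it is cheap and concerns the organ that the protocol singles out.

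**What to change.** 1. In SAP 12.1, limit the exclusion of unscheduled data to by-visit descriptive summaries.
2. In Tables 14.3.4 and 14.3.7.2, add one row per parameter and arm that counts patients with a potentially clinically important value at any time after baseline, unscheduled results included. Show amylase and lipase explicitly. State that n in this row is patients, since both templates now define n as results.
3. Keep the scheduled-visit rows beside the new row, and footnote it: symptom-triggered sampling may differ between arms, so the row is to be read with the scheduled counts.

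The cost is one sentence and one row in each of two shells. It needs no new data, provided that unscheduled results carry the same CRF mark of clinical significance as planned ones, and it does not affect patient management. If the SAP can no longer be amended, SAP 3 already allows a supplementary analysis identified as such in the study report.
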